4.10.1.1 Sensitivity Analysis

To check that primary efficacy findings are robust, sensitivity analyses will be performed, as follows:

- The MMRM described in [section 4.10.1](#) will be repeated using the PPS, and presented in a similar manner. Of note, patients who had a PKAN-ADL administration error will be excluded from the PPS.
- In addition, analysis of covariance (ANCOVA) models will be applied to change from baseline in PKAN-ADL total scores assessed after 3, 6, 12, 18, and 24 weeks of treatment. For each week analyzed, the model will include treatment and age group (pediatric, adult) as fixed effects, and baseline PKAN-ADL total score as a covariate.

The ANCOVA analysis will be performed for the Double-Blind FAS using PROC GLM in SAS. The models will be run using the observed case (OC) and last-observation-carried-forward (LOCF) procedure to account for incomplete data. In each case, estimates of adjusted treatment means and the adjusted mean difference between treatment groups will be presented at each time point, along with the two-sided 95% CIs and p-values for treatment comparisons.

The LOCF procedure will be applied for post-baseline observations of the PKAN-ADL total score in which more than 20% of the items are missing and cannot be imputed in the manner described in [Section 4.1](#). The last observed post-baseline PKAN-ADL total score, including those from unscheduled visits, will be imputed to replace the missing value of PKAN-ADL total score.

The PROC GLM SAS coding, to be run for each visit and each OC/LOCF procedure, is as follows:

```
proc glm data=DATA;  
    class TRT AGE;  
    model week_x_total=base_score TRT AGE / solution;  
    lsmeans TRT/ pdiff stderr;
```

run;

4.10.1.2 Handling of Dropouts and/or Missing Data

The MMRM approach used for the primary efficacy analysis accounts for data “missing at random” through a variance covariance structure. The ANCOVA models (described above) employ both the OC and LOCF methods to explore the impact of drop-outs and missing data. However, mixed models have been shown to be less biased under Missing at Random (MAR) and Missing Completely at Random (MCAR) conditions compared with LOCF or Completer analyses (Prakash, 2008).

To assess the appropriateness of the MAR assumption, additional sensitivity analyses using a tipping point approach will be used to assess how extreme and detrimental outcomes among patients with missing data must be to overwhelm the treatment effect attained in those patients who had complete data. In these analyses, the same basic analytic model will be used as in the primary analysis, but a multiple imputation approach will be implemented to allow for varying impact of missing data by incorporating a shift parameter in the imputation model. The range of values for the shift parameter will explore the varying missing data assumptions, from MAR to Missing Not at Random (MNAR), including the scenario where the imputation model is completely based on the control group (i.e., control-based imputation).

Following the approach described in Ouyang (2017), the following imputation procedures will be implemented:

1. Intermittent missing values before a discontinuation event (i.e., discontinuation of randomized therapy or early permanent dropout): The MAR assumption is reasonable for intermittent missing values before a discontinuation event since the values of the endpoint before and after the intermittent missing value are known. Imputation of intermittent missing data will be accomplished using the Markov Chain Montel Carlo (MCMC) option in SAS PROC MI by treatment group to impute intermittent missing data without a monotone missing pattern, prior to performing imputation of values following the discontinuation event.
2. Missing data following a discontinuation event (i.e., discontinuation of randomized therapy or early permanent dropout): Imputation of the post-discontinuation missing data by treatment group under the assumption of MAR using the regression option from the monotone statement of SAS PROC MI. Baseline and post-baseline scheduled visits will be used in the regression option to impute the missing values.
3. Steps 1 and 2 will be repeated to generate 30 multiply-imputed datasets.

4. For the fosmetpantotenate-treated patients, the post-discontinuation imputed values from step 3 will be made worse by subtracting a delta defined as $k=100\%$ times the treatment differences (means) obtained for the post-discontinuation visits obtained from the specified mixed model analysis (i.e., the analytic model) of the endpoint. No adjustment from the MAR assumption will be implemented for the placebo-treated patients (i.e., $k = 0\%$).
5. The mixed model (i.e., the analytic model) analysis described for the endpoint will be performed on each set of the newly “complete” data (observed data plus imputed values).
6. Using Rubin’s approach ([Rubin 1987](#)), the estimated treatment effects are combined across imputations. This will be accomplished using SAS PROC MIANALYZE.
7. Repeat steps 4 through 6 with increasing values of k (e.g., 120%, 140%...200%...) until the significance of the pre-specified analysis assuming MAR is overturned (e.g., from p -value <0.05 to p -value ≥ 0.05). The worsening by k times the treatment differences is applied to all the post discontinuation imputed values for each set of “complete” data from step 3. As an example, if a fosmetpantotenate patient had 2 post-discontinuation visits imputed, the values of both of these 2 imputed visits would be made worse by subtracting k times the fosmetpantotenate versus placebo treatment differences at these 2 visits.

The iterations for each value of delta will be summarized in a table where the estimated treatment differences for the treatment comparisons will be presented together with 95% confidence intervals for the differences and p -values for the treatment comparisons.

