2.7 Pharmacogenomics

Pharmacogenomic assessment may be performed on blood samples drawn at screening for drug metabolizing enzymes, transporters, or indicators of therapeutic response or safety. These assessments will only be performed where local regulations permit and where approved by the site's Institutional Review Board/Independent Ethics Committee (IRB/IEC), and will be subject to separate consent/assent by the patient/parent/legal guardian as appropriate.

3 Overall Study Design

This is a pivotal, randomized, double-blind, placebo-controlled, multi-center, 2-arm study evaluating 24 weeks of treatment with fosmetpantotenate or placebo in patients with PKAN aged 6 to 65 years, with a 278 week open-label extension.

Eligible patients will be randomized in a 1:1 ratio to receive either fosmetpantotenate or placebo for a 24-week double-blind period; randomization will be stratified by screening weight and age group (pediatric, adult), as reported by Interactive Web Response System (IWRS). In Protocol Version 1, Pediatric is defined as ' <19 ' and Adult is defined as ' ≥ 19 .' In subsequent versions of the Protocol, Pediatric is defined as ' <18 ' and Adult is defined as ' ≥ 18 '.

Treatment in the double-blind period will begin with dose escalation for Days 1-3, followed by the full dose 3 times daily (TID) starting on Day 4. Matching placebo will be given according to the same dose escalation sequence as active investigational product. Study visits during the double-blind period are scheduled at baseline (within 1 to 2 days prior to the start of the double-blind treatment), Days 1 through 4, and Weeks 3, 6, 12, 18, and 24. See Protocol Appendix A ([Table 15.1-1](#)) for the schedule of assessments performed during the double-blind period.

After completing the double-blind period, patients will be eligible to receive open-label fosmetpantotenate for up to 278 weeks. During the open-label period, study visits are scheduled at Weeks 27, 30, 36, 48, 60, 72, 84, 96, 108, 120, 146, 172, 198, 224, 250, 276, and 302. See Protocol Appendix A ([Table 15.1-2](#)) for the schedule of assessments performed during the open-label period.

In total, patients will be in the study for approximately 302 weeks, with 24 weeks in the randomized, double-blind treatment period and 278 weeks in the open-label period.

4 Statistical Methodology

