4.2 Determination of Sample Size

It is estimated that a total of 74 patients (37 in each treatment group) will provide approximately 80% power to detect a 3-point difference between groups in the average change from baseline score for the PKAN-ADL, based on Student's t-test with alpha=0.05 (two-sided); this calculation assumes a standard deviation of 4.5 points for the change from baseline scores. Allowing for 10% attrition, a total of 82 patients will be randomized to achieve the target sample size of at least 74 patients completing the double-blind period of the study.

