Patients with PKAN-ADL administration errors will be included in the Double-Blind FAS, but excluded from the PPS, as per [Section 4.5](#). Imputation rules for the data affected by the translation issue can be found in [Section 4.1](#).

The linear mixed-effect model will be implemented using PROC MIXED in SAS with the restricted maximum likelihood (REML) estimation method. An unstructured variance-covariance matrix will be used to model the within-patient errors. [Note: In the unlikely event that the computational algorithm fails to converge, the following structures will be executed in the order specified (essentially in decreasing order of complexity) until convergence is achieved: Toeplitz with heterogeneity, autoregressive with heterogeneity by Week, compound symmetry with heterogeneous variances by Week, autoregressive, Toeplitz, and compound symmetry without heterogeneous variances by Week.]

Significance tests will be based on least squares means (LSMs) using Type III sum of squares. The Kenward and Roger method will be used for calculating the denominator degrees of freedom for tests of fixed effects.

The PROC MIXED SAS coding is as follows:

```
proc mixed data=DATA;
    class TRT WEEK PATIENT;
    model C_score = BASE_score AGE TRT WEEK TRT*WEEK / solution
    ddfm=kr;
    repeated WEEK / subject=PATIENT type=un;

run;

where:
    TRT = treatment group (0 = placebo, 1 = fosmetpantotenate)
    WEEK = week 3, 6, 12, 18, 24
    AGE = age group (0=Pediatric, 1= Adult)
    C_score = change in score from baseline
    BASE_score = baseline score
```

The LSMS for each treatment, the difference between the LSMSs, and the standard error (SE) and 95% confidence interval (CI) associated with the difference will be reported at each study visit. The primary treatment comparison will be based on the test of contrast between treatment effects using the LSM estimate at Week 24, adjusted for baseline score and age group from the Type III analysis.

To estimate the mean change from baseline for PKAN-ADL total scores in each treatment group (placebo or fosmetpantotenate) at Week i ($i = 3, 6, 12, 18$, and 24), the following estimate statement (as an example) will be utilized:

```
estimate 'Placebo Group at Week 24'
    intercept 1
    AGE        <proportion in age group=0  proportion in age group=1>
    BASE_score <mean of BASE_score>
    TRT        1 0
    WEEK       0 0 0 0 1
    TRT*WEEK   0 0 0 0 1
                0 0 0 0 0 / cl;

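### The tipping-point analysis needs more imputations, a recorded seed and small-sample degrees of freedom for a reproducible, slightly less favourable tipping value

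*SAP*

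**What the plan says.** SAP section 4.10.1.2 sets out a seven-step tipping-point analysis of the primary endpoint.

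- Steps 1 and 2 impute intermittent and post-discontinuation values by treatment group. Step 3 fixes the number of imputations: "Steps 1 and 2 will be repeated to generate 30 multiply-imputed datasets".
- Step 4 worsens the post-discontinuation imputed values in the fosmetpantotenate arm only, by k times the treatment difference, starting at k = 100%.
- Step 6 cites Rubin (1987) and says "the estimated treatment effects are combined across imputations. This will be accomplished using SAS PROC MIANALYZE".
- Step 7 begins "Repeat steps 4 through 6 with increasing values of k (e.g., 120%, 140%...200" and continues until p passes from below 0.05 to 0.05 or above. Estimates, 95% CIs and p-values are tabulated for each delta.

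The section gives no random seed, no check of Monte Carlo error, and no complete-data degrees of freedom for the pooled test. The primary MMRM in section 4.10.1 does use a small-sample method: "The Kenward and Roger method will be used for calculating the denominator degrees of freedom for tests of fixed effects".

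**The concern.** Thirty imputations can be adequate for a pooled estimate and its standard error. Here, though, the quantity of interest is the k at which p crosses 0.05. Only the imputed active-arm values are shifted, so the treatment difference responds weakly to k, and a small simulation error in the estimate becomes a larger error in k.

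The degrees of freedom are a separate matter. The 1987 rule assumes a large complete-data sample. With 82 patients it gives a near-normal reference distribution, whereas the primary test uses Kenward-Roger. The imputation table is then judged by a slightly more lenient standard than the analysis it is meant to stress.

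What is at stake is whether the tipping point can be reproduced, and whether it is slightly flattering, in the SAP's only missing-not-at-random analysis of the primary endpoint.

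**Working it through.** **Inputs.** SAP section 4.2 gives "approximately 80% power to detect a 3-point difference between groups", two-sided alpha 0.05, and "this calculation assumes a standard deviation of 4.5 points for the change from baseline scores", with 10% attrition and 82 randomised. SAP section 3 gives "Eligible patients will be randomized in a 1:1 ratio", so 41 per arm. Section 4.10.1.2 gives m = 30. Visit correlation, dropout timing, the share actually missing and the fraction of missing information (λ) are assumptions.

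**The plan's own figure.** With 37 per arm, SE = 4.5 × √(2/37) = 1.046 and 3/1.046 = 2.87. The noncentral t distribution gives power 0.808, which agrees with the SAP. The attrition allowance also agrees: 82 × 0.9 = 73.8.

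**How far k moves the estimate.** With 10% of the active arm shifted, 100 points of k move a 3-point difference by 0.10 × 3 = 0.3. The complete-data SE with 41 per arm is 4.5 × √(2/41) = 0.99.

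**Seed noise by hand.** The Monte Carlo SD of the pooled estimate is √(λT/m), with T = 0.99²/(1 − λ). Dividing by 0.3 and multiplying by 100 converts it to points of k.

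| λ | SD of estimate, m = 30 | in points of k | m = 500, points of k |
|---|---|---|---|
| 0.03 | 0.032 | 11 | 3 |
| 0.10 | 0.060 | 20 | 5 |

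**Degrees of freedom by hand.** The 1987 rule gives (m − 1)/λ²: 29/0.10² = 2,900 and 29/0.05² = 11,600. The critical value is about 1.96. The Barnard-Rubin adjustment uses ν_obs = [(ν₀ + 1)/(ν₀ + 3)] × ν₀ × (1 − λ), combined with the 1987 value by adding reciprocals. Taking ν₀ = 78 (82 patients less four ANCOVA parameters) and λ = 0.10:

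- ν_obs = (79/81) × 78 × 0.9 = 68.5
- combined df = 1/(1/2,900 + 1/68.5) = 66.9, critical value 1.996

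With λ = 0.05 the result is 71.8 and 1.994. At about 68 df, a nominal 5% test judged against 1.96 has size 5.4%. The CI is about 1.8% too narrow (1.960/1.995 = 0.982). In points of k, 0.035 × 0.99/0.3 × 100 is about 12. Significant datasets show a larger difference; at 3.5 points, 100 points of k move it by 0.35, and the figure is about 10.

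**Simulation.** Steps 2 to 7 were simulated with 41 per arm, true difference 3 and SD 4.5. Imputation was by Bayesian regression within arm, and Week 24 ANCOVA stood in for the MMRM. Each row uses 150 datasets significant under missing at random, with 60 seeds each, at m = 30. Entries are medians.

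| Missing per arm; visit correlation | Tipping k | Seed SD (points) | Pairs of seeds on different grid values | Two or more steps apart | Overstatement from df (points) |
|---|---|---|---|---|---|
| 10%; autoregressive 0.8 | about 330% | 14 | 62% | 13% | 8 |
| 10%; exchangeable 0.5 | about 330% | 15 | 63% | 17% | 9 |
| 10%; exchangeable 0.8 | about 320% | 10 | 53% | 3% | 8 |
| 5%; autoregressive 0.8 | about 570% | 19 | 70% | 27% | 14 |
| 20%; autoregressive 0.8 | about 176% | 12 | 53% | 3% | 5 |

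A second simulation at 10% missing gave a seed SD of 14 to 17 points, rising to 22 to 28 when k tipped below 200%. Its 1987 df were 3,300 to 5,700 against 68 to 70 adjusted, and k was overstated by about 9 points. A third, limited to significant results with t from 2.1 to 3.2, gave a seed SD of about 21 (range 10 to 37) and an overstatement of about 11.

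**Separating the causes.** Using m = 30 shifted the mean tipping k by under 1 point, so it adds noise and almost no bias. In the 10%, autoregressive case:

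- m = 500 cut the seed SD to about 4 points and differing pairs to a median of 20%.
- m = 1000 gave about 2 points and a median of 0% (90th percentile 41%).
- The overstatement stayed at 8 to 9 points in both, because it comes from the degrees of freedom.

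**The case against.** The strongest reply is that the effect is small where it is most often seen. With k tipping near 330%, a seed SD of 14 points is about 4% of k, and an 8-point overstatement is under half a step. Twenty points of k correspond to 0.06 points on a 48-point scale. The grid is given only as an example, and the table shows estimates, CIs and p-values at each delta, so a reader can see how gradually p approaches 0.05. All of this stands.

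It is also true that the SAP names no degrees of freedom for pooling and does not rule out supplying them. The analytic model already yields Kenward-Roger values. The 1987 degrees of freedom are an inference from the cited rule with no adjustment mentioned. That stands as a limit on the second part, but it is also the reason to state the option.

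A reader might infer three stronger things that the documents and the arithmetic do not support:

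- **That the tipping point typically moves a full 20-point step with the seed.** At 10% missing the typical SD is below one step. It reaches about 20 or more mainly for borderline results.
- **That 30 imputations inflate the tipping point.** They do not; only the degrees of freedom do.
- **That the trial's efficacy conclusion is exposed.** It rests on the Week 24 MMRM contrast and the gatekeeping in section 4.10.4. A primary p between about 0.050 and 0.054 could look significant in the imputation table, but the primary p would govern, and step 7 presupposes significance under missing at random.

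**Conclusion.** The point holds as a cheap improvement to a sensitivity analysis. The two causes act separately: seed noise can go either way, while the degrees-of-freedom effect always makes the result look more robust. Either can shift the reported grid value; at 10% missing, the degrees of freedom alone changed it in about 40% of runs. Neither usually changes the reading when k tips far above 100%. They matter when k tips at about 100% to 160%, where one step affects how robust the result appears.

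The sizes rest on the assumed visit correlations, dropout pattern and missing share, and on ANCOVA in place of the MMRM. Fewer missing values, for instance if patients who stop treatment keep attending as the protocol encourages, raise both the tipping k and its error in points. The 5% row shows this.

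**What to change.** In step 3, replace 30 with at least 500 imputed datasets, or 1000 if near-complete stability on a 20-point grid is wanted, and state a fixed seed to be recorded with the output. In step 6, specify that PROC MIANALYZE receives the complete-data (Kenward-Roger) degrees of freedom through EDF=, so that the Barnard-Rubin adjustment applies and the p-values and CIs are on the same small-sample footing as the primary test. Both changes are needed, since more imputations do not correct the degrees of freedom. The cost is two lines of SAP text, computing time on 82 patients, and a tipping point lower by about 8 to 11 points of k at 10% missing.

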4.10.1.3 Exploratory Subgroup Analysis

The influence of potential prognostic factors on the primary efficacy endpoint will be assessed via the mixed model described for the primary analysis, using the Double-Blind FAS. That is, the mixed model will include baseline PKAN-ADL total score and additional prognostic factors (each considered univariately) as covariates, with treatment group, Week, treatment*Week, and treatment*prognostic factor as fixed effects. The factors to be assessed are as follows:

- Age at screening (pediatric, adult)
- Age at disease onset ($<\text{median}$, $\geq \text{median}$)
- Sex (male, female)
- Baseline PKAN-ADL total score (1st quartile, 2nd quartile, 3rd quartile, 4th quartile).
- Duration of Illness ($<\text{median}$, $\geq \text{median}$)

Factors found to have a significant effect on response ($p < 0.10$) will be examined further, to understand the relationship between prognostic factor and response. For all factors, the

LSMs for each treatment, the difference between the LSMs, and the standard error (SE) and 95% confidence interval (CI) associated with the difference will be reported at each study visit, using the MMRM which includes the given factor as a covariate.

4.10.2 Secondary Efficacy Endpoint

Part III of the UPDRS consists of 27 items, which correspond to 14 domains related to motor abilities such as tremor, stability, and bradykinesia. Each item has responses ranging from 0-4, with a higher value indicating greater disability. To compute the UPDRS Part III total score, responses are summed across the 27 items, and accordingly, will range from 0-108. For domain totals, responses will be summed across all of the items in a given domain (when domain corresponds to multiple items).

For analysis purposes, data from the pediatric and adult age groups will be pooled. All descriptive summary tables will be repeated using age group as a subgroup.

Descriptive statistics will be presented for the UPDRS Part III total score, with absolute and percent change from baseline, by treatment group for each visit of the double-blind period. For post-baseline assessments, categories for change from baseline UPDRS Part III total score (e.g., >0 , $=0$, <0 , ≤ -1 , ≤ -2 , ≤ -3 , ≤ -4), categories for percent improvement (i.e., decrease) in UPDRS Part III total score from baseline (i.e., $<0\%$, $=0\%$, $>0\%$, $\geq 10\%$, $\geq 20\%$, $\geq 30\%$, $\geq 40\%$, $\geq 50\%$), and categories for UPDRS Part III total score status (improvement, no change, or worsening) will be presented. These categories may be adjusted in a way that ensures that the categories contain at least 10% of patients. This will be run using the Double-Blind FAS and repeated using the PPS, as a sensitivity analysis.

Frequency tables will display change from baseline for each of the 14 domains, by treatment group for each visit of the double-blind period, using categories for change from baseline domain score (i.e., >0 , $=0$, <0 , ≤ -1 , ≤ -2 , ≤ -3), and categories for domain score status (improvement, no change, or worsening). These summaries will be run using the Double-Blind FAS and repeated using the PPS, as a sensitivity analysis.

The MMRM model described above for the primary efficacy endpoint will also be performed for the secondary efficacy endpoint: change from baseline UPDRS Part III total score. The LSMs for each treatment, the difference between the LSMs, and the standard error (SE) and 95% confidence interval (CI) associated with the difference will be reported at each study visit. The analysis will be based on the Double-Blind FAS, and will be repeated using the PPS, as a sensitivity analysis.

The ANCOVA models, as described in [section 4.10.1.1](#), will be run for change from baseline in UPDRS Part III total scores assessed after 3, 6, 12, 18, and 24 weeks of treatment for patients in the Double-Blind Full Analysis Set. The models will be run

using the observed case (OC) and last-observation-carried-forward (LOCF) procedure to account for incomplete data.

The exploratory subgroup analysis, as described in [section 4.10.1.3](#), will also be run for the UPDRS Part III total score.

Furthermore, a chi-squared test will be performed at each post-baseline visit to determine treatment differences between the percentages of patients who had a total score indicating improvement, no change, or worsening. Proportions, with estimated 95% CI, will be reported for each treatment group, along with a p-value corresponding to the treatment comparison.

Figures will be presented which show the UPDRS Part III total score for each visit during the double-blind period, as well as change from baseline score, by treatment group. This will be run using the Double-Blind FAS and repeated using the PPS.

A by-patient listing will be provided, which presents UPDRS Part III scores (total and for each of the 27 items) across all assessments in the double-blind and open-label periods for patients in the Double-Blind FAS.

